#### **5a. Affected Individuals:**

**Cognitive function** will be assessed with the Alzheimer's Disease Assessment Scale – Cognitive Subscale (ADAS-cog) (Rosen 1984), which is the most commonly used primary outcome measure in AD treatment trials. It is an 80-point scale that includes direct assessment of learning (word list), naming (objects), following commands, constructional Praxis (figure copying), ideational Praxis (mailing a letter), orientation (person, time, place), recognition memory and remembering test instructions.

**Physical performance** will be assessed with the Short Physical Performance Battery (SPPB), which was developed by the National Institute on Aging to provide an objective tool for evaluating lower extremity functioning in older adults. The test includes repeated chair stands, tandem

balance testing and 8' walking speed (Guralnik 1994). Several additional items from the Senior Fitness Test (SFT) will be added to assess flexibility (sit-and-reach) and mobility (8-foot up-and-go) (Jones & Rikli 2002).

**Fall-related self-efficacy** will be assessed with the Falls Efficacy Scale (FES), which is a 10-item scale that has been validated in individuals with cognitive impairment (Hauer 2010). We are using a modified version that includes a 4-point Likert scale rather than a 10-point scale to increase ease of use.

**Mood** will be assessed with the Geriatric Depression Scale (GDS), a standard measure that includes 15 yes/no questions and has been validated in people with and without cognitive impairment (Sheikh and Yesavage, 1986)

**Quality of life** will be assessed with the Quality of Life Scale in Alzheimer's Disease (QOL-AD), which is a brief, 13-item measure that obtains input from both the individual and the caregiver (Logsdon 1999). Scores may range from 13-52 points.

**Exploratory Outcome: Near Infrared Spectroscopy (no longer being performed).** This assessment method has been developed in the past 30 years but is exploratory for our setting. The NIRS method has been used in combination with the Verbal-Fluency Task in Alzheimer's patients before, (M.J. Herrmann, A.-C. Ehlis, A.J. Fallgatter: Frontal activation during a verbal-fluency task as measured by near-infrared spectroscopy. *Brain Research Bulletin* 61 (2003) 51–560), but it has never been applied in a longitudinal study with our population. It will be done once at baseline and once with the other tests at the end of the 3-month intervention. It is a noninvasive measure that uses a small (1x2 inch) flexible patch that uses adhesive tape to stick to the forehead of the affected individuals. The patch is connected to a laser light source and a sensor that can measure regional brain oxygenation. The patch is connected by 2 lengthy thin cables to a monitor and a laptop where the data can be downloaded to an encrypted flash drive. The measure will be used in combination with the Verbal-Fluency Task. After the subjects seemed to be relaxed, a baseline measurement of approximately 60 s will be conducted. After a verbal request to open their eyes now, the participants will be instructed to pronounce in overt speech as many nouns as possible beginning with the letters "A," "F," and "S" or--after the exercise demonstration-- with the letters "E," "G" and "P".(Lezak, Muriel Deutsch (1995) . *Neuropsychological assessment*. Oxford [Oxfordshire]: Oxford University Press. **ISBN 0-19-509031-4.**) No repetitions or proper nouns are allowed. Each of these three conditions (different starting letters) will last 60 s. The correct verbal responses of the subjects are recorded and used as a measure of behavioral performance. (A more detailed description of the device is attached)

### **5b. Caregivers.**

**Affected Individual's physical function** will be assessed with the Disability Assessment for Dementia (DAD) (Galinas and Gauthier, 1994), which is a standard measure that asks caregivers to rate the participant's disability with 17 basic and 23 instrumental activities of daily living over the past 2 weeks. The DAD has high established validity and high test-retest reliability (ICC, 0.96), inter-rater reliability (ICC, 0.95), and internal consistency (Chronbach's alpha, 0.96).

**Affected Individual's dementia-related behaviors** will be assessed with the Neuropsychiatric Inventory (NPI), which is a 144-point informant-based questionnaire that assesses 12 behavioral domains common in dementia including frequency, severity and impact on caregiver distress (Cummings 1997).

**Affected Individual's falls** will be assessed based on caregiver report of number of falls in the previous 4 months.

**Affected Individual's quality of life** will be assessed with the Quality of Life Scale in Alzheimer's Disease (QOL-AD), which is a brief, 13-item measure that obtains input from both the individual and the caregiver (Logsdon 1999). Scores may range from 13-52 points.

**Caregiver burden** will be assessed with the Caregiver Burden Inventory (CBI), which is a 96-point scale that includes 24 items and 5 domains (Novak 1989).

**Caregiver mood** will be assessed with the GDS.

**Positive feelings about caregiving** will be assessed with the Positive Aspects of Caregiving scale, a standard measure that asks caregivers to rate their agreement/disagreement with 11 statements about positive aspects of caregiving on a 5-point Likert scale (disagree a lot .... agree a lot). (Tarlow 2004)

**Caregiver health status** will be assessed with the Medical Outcomes Study Questionnaire Short Form 36 Health Survey (SF-36), which includes 10 items that are used to create eight scaled scores related to vitality, physical functioning, bodily pain, general health perceptions, physical role functioning, emotional role functioning, social role functioning and mental health. The SF-36 has high reliability (0.8-0.9) and has been validated in numerous adult populations.

**Affected individual's urinary incontinence** will be assessed with questions about the frequency and severity of accidental urine leakage.

**6. Qualitative data.** Exercise instructors or other research staff may record qualitative observations of participants and/or caregivers including changes in movement abilities, emotional state, or cognitive function of participants within the class setting over time, and in response to specific exercise interventions as they are introduced. Comments made by participants and caregivers related to the exercise class may also be recorded. Semi-structured interviews also may be conducted with caregivers to assess feasibility and acceptability of the program, barriers to home practice and suggestions for improvements.

**7. Compliance, co-interventions and adverse events.** Compliance will be assessed based on class attendance. In addition, caregivers will be asked to complete weekly reflection journals. Monthly check-in calls will be performed with caregivers to assess for adverse events, falls and co-interventions (e.g., changes to medications or daily routine) and to address issues related to non-compliance and barriers to practice. If caregivers request, monthly check-ins may be conducted via mail, email, fax or text. Caregivers will be informed that these modes of communication may increase their risk of loss of privacy. Mail, email, fax and text communications will include a confidentiality statement. The minimum amount of identifying information will be included in all communications. Study forms will include unique study ID numbers only.

**8. Video-Recording.** Some exercise classes and assessments may be video-recorded for quality control and educational purposes. Study participants will be able to consent to video recording for research and educational purposes (private viewing only) or public release of video recordings (public + private viewing). If any person who has not consented enters the video frame, this section will be deleted. Other persons may be staff at the study sites. Video recordings will be saved in a MyResearch folder only in the edited version (without any non-consented person in the frames). All other video recordings will be deleted from the camera after downloading on a secured server or an encrypted external hard drive stored in a secure locked file cabinet and will not be stored on any computers.

**9. Post-intervention.** Study participants will be provided with an illustrated booklet and access to videos (e.g., DVD or YouTube) to support home-based practice. Findings from the study may be provided to subjects and caregivers in aggregate form (i.e., without identifying individual subjects). Study participants will sign separate consent for future contact.

**10. Qualitative Interview Substudy.** Study participants who have completed the intervention and have agreed to future contact related to this research study will be contacted by telephone and asked if they would be interested in participating in a substudy that would involve semi-structured interviews conducted in their homes. Two research team members (including at least one exercise instructor) will conduct the home visits and interviews. This sub-study will require participants to sign a separate consent form and to consent/assent specifically for this sub-study. The topic of the interview is to solicit answers to (1) questions about motivators and barriers to home exercise practice and (2) questions about participants' wishes for written and/or electronic material that may support home practice. We will initially recruit 5 dyads for a 1-hour interview. Semi-structured interviews will follow an interview guide, will be audio-recorded and transcribed. We will develop new support material following the suggestions of the interviewees. We are planning to improve the exercise brochure and create a series of new and shorter video clips for DVD or YouTube according to the feedback of the participants. This material will be given to these participants for a month of home application followed by a second interview and asking for a written evaluation. Participants will also answer a brief questionnaire about facilitators and barriers for home practice and use a log for daily entries about their exercises and study-related movements. The second interview may prompt iterative revision of our support material, which we will provide to a second group of 5 dyads undergoing the same two interviews. Following the completion of all interviews, the support material will undergo a final professional production which we plan to include in a larger multi-site study of our Paired PLIE Program.

Audio recordings will be stored and--after study completion--deleted the exact same way as the video-recordings.

If you have a procedure table, attach it to the submission with your other study documents.

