## 11.0 Study Design

### 11.1 \* Study design (Help Text updated 9/13):

We propose to perform a randomized, controlled trial (RCT) with a delayed start design to examine the effects of the Paired PLIÉ program in individuals with cognitive impairment and their care partners over 9 months. Study participants will be 60 pairs of individuals with mild-to-moderate cognitive impairment and their primary care partners. Study pairs will be enrolled in blocks of 10 and will be randomly assigned to Group 1 (immediate start, n=5) or Group 2 (3-month delayed start, n=5). Pairs randomized to Group 1 will participate together in the Paired PLIÉ program 2 days/week for 12 weeks (24 classes total) while pairs randomized to Group 2 will continue with their usual activities. After 3 months, Group 1 will transition into a maintenance phase, and Group 2 will participate in the Paired PLIÉ program 2 days/week for 12 weeks. Outcome data will be collected in all study participants at baseline and 3, and 6 months. We have partnered with local community-based organizations that have agreed to serve as study sites and to assist with recruitment efforts.

We will conduct a sub-study with semi-structured interviews in a sub-sample of our participants. The goal is to assess motivations and barriers for home practice of the exercises taught in the intervention classes and to develop improved support materials (brochures, video clips on DVD and/or YouTube) according to feedback from participants.

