#### **12.3 Statistical analysis:**

All primary analyses will be performed using intent-to-treat principles. Baseline characteristics will be compared using descriptive statistics (e.g., frequency tables and percentages for categorical variables; means, medians, standard deviations, ranges for continuous variables), and p-values will be calculated using appropriate statistical tests (e.g., chi-square, t-test, Mann-Whitney). Our primary analytic approach will be mixed effects linear regression which will enable efficient estimation of intervention effects and inclusion of all subjects in intent-to-treat analyses. Analyses will focus on differences in outcomes between the groups over time. Fixed effects terms will be included for group (immediate vs. delayed start), time (0, 3, 6 or 9 months), and the interaction between group and time, with time modeled as a dummy variable. Subjects and cohorts will be modeled as random effects. Models also will adjust for any baseline differences between groups that may occur by chance. Covariates will be included to adjust for any co-interventions that may occur (e.g., medication changes). Sensitivity analyses will be performed to determine the effects of compliance on intervention effects. Graphs and diagnostic tests will be used to assess for outliers and influence points. Line plots will be used to visually examine change over time by group.

Sub-Study: We will conduct qualitative analyses of the transcribed audio recordings from 10 interviews..

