### 13.2 Preliminary studies:

Our group has recently pioneered a novel, multi-domain program called Preventing Loss of Independence through Exercise (PLIÉ, pronounced 'plee-ay'). PLIÉ integrates physical activity (training of procedural memory for basic daily activities such as transitioning safely between sitting and standing), cognitive stimulation (mindful body awareness), social engagement (group movement and sharing of in-the-moment experiences), music, and caregiver education (monthly home-visit). We studied PLIÉ in individuals with mild to moderate dementia who were attending an adult day program in San Francisco, CA, and found evidence that those who participated in PLIÉ for 45 minutes, 2-3 days per week for 4 months (total: 26-39 hours) experienced improvements in a wide range of outcomes compared to a Usual Care (UC) control group that participated in standard chair-based exercises. Standardized, between-group effect sizes were moderate to large on validated measures of quality of life (0.83), cognitive function (0.76) and caregiver burden (0.49).

Although PLIÉ was originally designed and tested in an adult day care setting, most people in the community do not have access to a day care center, are concerned about the stigma associated with day care or are unable to afford it. **There is a huge need for innovative, rigorously-tested programs that can be performed together by affected individuals and their care partners, either in group settings or at home.** The Paired PLIÉ Program was specifically designed to address this critical need in the community. Over the past year, we have systematically created the Paired PLIÉ program by adapting the original PLIÉ protocol to be performed by dyads of affected individuals and care partners.

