**5. Assessments.** We will perform a variety of standard measures in all participants and caregivers at baseline, 3, 6 and 9 months. Data will be collected separately in affected individuals and caregivers to maximize the validity of data collected (e.g., to ensure that caregivers do not 'help' affected individuals with answers to questions and feel comfortable providing information about issues such as difficult behaviors or levels of stress). Affected individuals assessments will take place at the study site. Caregiver assessments will primarily consist of questionnaires that can be self-administered. Therefore, these assessments may occur in person, by phone, or may be returned by email or standard mail, depending on caregiver preference. The first line of communication will be via telephone or in person to minimize the risk of loss of privacy. At the caregiver participant's request, further communication may be conducted via mail, email, fax or text. Caregivers will be informed that these modes of communication may increase their risk of loss of privacy. Mail, email, fax and text communications will include a confidentiality statement. The minimum amount of identifying information will be included in all communications. Study forms will include unique study ID numbers only.

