#### Caregiver

- Consent/eligibility visit (1 hour)
- Baseline assessment (1 hour)
- Intervention (1 hour, 2 days/week for 12 weeks: 24 hours total)
- Home visits (3 visits, 1 hour each: 3 hours total)
- Monthly telephone check-ins (9 calls, 20 minutes each: 3 hours total)
- Post-intervention assessments (3, 6 and 9 months, 1 hour each: 3 hours total)
- Total: 36 hours over 12 months
- Home practice: additional 1-2 hours/week

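### Falls are recalled over 4 months at visits 3 months apart, so the month-6 count includes one month from before the groups change roles

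*Combined protocol and SAP*

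**What the plan says.** Section 16.1, item 5b, defines the falls measure: falls "will be assessed based on caregiver report of number of falls in the previous 4 months". Item 5 of the same section schedules measures "in all participants and caregivers at baseline, 3, 6 and 9 months", and section 16.6 lists the same follow-up visits for caregivers. Section 11.1 names only baseline, month 3 and month 6. On either schedule, visits are 3 months apart.

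Section 11.1 also sets the switch: "After 3 months, Group 1 will transition into a maintenance phase, and Group 2 will participate" in the classes from then on. Section 12.3 gives one general model for all outcomes, with terms for group, "time (0, 3, 6 or 9 months), and the interaction between group and time, with time modeled as a dummy variable". That model yields a group contrast at each visit.

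Falls are collected by a second route. Section 16.1, item 7, says: "Monthly check-in calls will be performed with caregivers to assess for adverse events, falls" and co-interventions. Nothing links these calls to the falls outcome in item 5b, and nothing says how overlapping recall periods are handled.

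**The concern.** A delayed-start design is read by phase. Up to month 3, Group 1 is in class and Group 2 is not. From month 3 to month 6, Group 2 is in class and Group 1 is in maintenance. A count that reaches back 4 months from a month-6 visit crosses that boundary and mixes the two phases, with the groups in opposite roles in the month that is carried over. Likewise, the month-3 count reaches back to before baseline.

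At stake is the reading of the falls results, above all at month 6. If Group 1 keeps its benefit, two equal fall rates would look different. If it loses the benefit, the true difference would be understated. Falls are a secondary matter here, but the program includes balance exercises aimed at them (section 16.1, item 4), and section 17.1 lists falls as a risk.

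**Working it through.** The plan states no figure for falls to reproduce; the sample-size figures in section 14.4 do not concern them.

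**Inputs from the plan.** Recall W = 4 months (16.1, item 5b). Visits at t = 0, 3, 6 and 9 (16.1, item 5). Switch at month 3 (11.1).

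**Assumed inputs, for illustration only.** L is the monthly fall rate under usual activities. c is the rate ratio during classes, taken as constant at 0.5, 0.7 or 0.9. m is the rate ratio after classes, with m = c if the benefit is kept and m = 1 if it is lost. The documents give none of these.

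**Step 1: windows.** Each count covers [t − 4, t]: [−4, 0], [−1, 3], [2, 6] and [5, 9]. Adjacent windows share 4 − 3 = 1 month. With 3-month recall they would be [−3, 0], [0, 3], [3, 6] and [6, 9], with no overlap.

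**Step 2: month 6, ratio of Group 1 to Group 2.**
- 4-month recall: (c + 3m) / (1 + 3c)
- 3-month recall: 3m / 3c = m / c

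For c = 0.5 with the benefit kept: (0.5 + 1.5) / (1 + 1.5) = 2.0 / 2.5 = 0.80, against a true 1.00. With the benefit lost: (0.5 + 3) / 2.5 = 1.40, against a true 2.00.

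| c | Kept: true | Kept: as recorded | Lost: true | Lost: as recorded |
|---|---|---|---|---|
| 0.5 | 1.00 | 0.80 | 2.00 | 1.40 |
| 0.7 | 1.00 | 0.90 | 1.43 | 1.19 |
| 0.9 | 1.00 | 0.97 | 1.11 | 1.05 |

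**Step 3: does subtracting baseline help at month 6?** The windows [2, 6] and [−4, 0] share no time, so nothing cancels. The group difference in change of raw counts is L(c + 3m) − L(1 + 3c), against L(3m − 3c) with 3-month recall. The shift is L(c − 1). At c = 0.5 a true 0 appears as −0.5L if the benefit is kept, and a true +1.5L appears as +1.0L if it is lost. If the effect varies over the class months, only its value in month (2, 3] counts. The shift is one third of the month-3 effect when the monthly effects are equal, one sixth if they run 3:2:1, and one half if they run 1:2:3.

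**Step 4: month 3, raw counts.** N[−1, 3] − N[−4, 0] = N[0, 3] − N[−4, −1], because month [−1, 0] is in both counts. At a constant background rate, the expected group difference is 3L(c − 1), the same as with 3-month recall. This needs the shared month to be reported the same way on both occasions.

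**Step 5: month 3, rates.** As a follow-up rate or rate ratio, the count includes one month before baseline, so the ratio is (1 + 3c) / 4. This gives 0.625 for 0.5, 0.775 for 0.7 and 0.925 for 0.9. Dividing the 4-month count by 4 does not cure this.

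**Step 6: visit timing.** If visits are d months apart, with 3 ≤ d ≤ 4, the overlap is 4 − d months. It is gone at d = 4.

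**The case against.** The strongest reply is that little hangs on this. Falls are in neither hypothesis (section 12.1) and not in the sample-size calculation (14.4), and no falls-specific analysis is described. The reading of month 6 as maintenance against class is inferred from the general model in 12.3. All of that stands and sets the severity. It does not remove the problem, because the mixed phases are in the data whichever model is fitted.

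A second reply is that the monthly calls already capture falls. They do, but item 5b defines the outcome by 4-month recall, and nothing substitutes the calls for it.

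A third is that actual timing may differ. Section 16.6 totals participation over 12 months, 11.1 enrols dyads in blocks of 10, and the gap between baseline and the first class is not stated. This makes an exact one-month overlap less certain. It does not establish 4-month intervals, since 16.1 and 16.6 still list months 3, 6 and 9. The caregiver form is not among the visible pages either, so its wording could not be checked.

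A reader might also infer that the overlap makes the reported standard errors or test size wrong by a definite amount. The documents do not support a figure. On correlation, section 12.3 says only: "Subjects and cohorts will be modeled as random effects". It gives no residual structure and does not mention count data. A raw 4-month count varies more than a 3-month count simply because the window is longer, so that difference should not be blamed on overlap.

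Finally, a reader might infer that the 4-month recall was copied from the pilot, whose program ran 4 months (section 13.2). That is possible, but the documents do not say so.

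**Conclusion.** The point holds and is minor. As written, on nominal dates, one of the four months in the month-6 falls count (25%) precedes the switch. If the program affects falls, the month-6 contrast is shifted by the effect in month (2, 3]. The ratios of 0.80 and 1.4 depend on an assumed class rate ratio of 0.5, a constant monthly effect, and the benefit being wholly kept or wholly lost. Weaker effects give smaller shifts, and no effect gives none.

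Two opposite readings of month 3 are tempting, and neither is right. One is that the month-3 result is untouched; that is true only of the point estimate for change in raw counts. The other is that it is diluted by a quarter whatever the analysis; that is true only of a follow-up rate or rate ratio. Nor does the overlap threaten the trial's main conclusions, because the outcomes named in section 12.1 do not include falls.

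**What to change.** In section 16.1, item 5b, set the falls recall to 3 months at baseline, and to the time since the last study visit (or 3 months) at follow-up. Make the caregiver form agree. Where windows differ in length, analyse falls per unit of time at risk.

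For 4-month follow-up counts already taken, use the monthly call records, where usable, to remove the overlapping month. The calls could instead become the follow-up source, with the 3-month question kept at baseline because no calls precede it. That alternative needs a condition. Section 16.1, item 3, blinds assessment staff, but the plan does not say who makes the calls or whether they are masked, and the calls also cover difficulties with practice. Use them as the outcome source only if call staff are masked, or acknowledge that they are not.

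The cost is one sentence in the protocol and, if the form follows the protocol, one line there. No extra contact is needed. The downside is that counts already collected cover a different exposure time, and they can be split by phase only if the call records are usable.
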